Inclusion criteria: (1) age 23-64.9 years, (2) BMI \geq 18.5, (3) 3+ hours per day of sedentary screen time, (4) insufficiently active as assessed by the Leisure-Time Categorical Item (see Appendix 4 – Screening survey, Leisure-time Categorical Item) (5) owns an Apple or Android smartphone or tablet, (6) have access to wireless internet at home or unlimited data plan, (7) willing to download StandUPTV smartphone application, (8) able to read/understand English, and (9) willing to be randomized.

Exclusion criteria: (1) current smoker; (2) major illness or pregnant, (3) physical activity contraindicated, (4) occupation requires media use or high amounts of physical activity 5) active drug abuse, (6) serious psychological disorder.

There will be no exclusion by sex. We will include participants without regard to race or ethnicity. Prisoners will not be included in the study because of the limitations on physical activity, access to the internet, television, smartphones/tablets and any other media. Undocumented individuals may or may not be included in the study, but no attempts will be made to verify the working credentials of study subjects, as it is unrelated to the purpose of the proposed study.

All screening questionnaires will be completed using an online screener delivered by REDCap (see Appendix 4 Screening survey) and then confirmed by telephone or video call.]

Number of participants

Approximately two hundred and forty (240) participants will be enrolled, 120 in the San Luis Obispo regional area and 120 in the Phoenix Metro area. We may consider enrolling outside those geographical areas as needed depending on recruitment success.

Recruitment methods

We will include traditional methods of recruitment including flyers on campus and through local community outlets and newspaper advertisements. But we will more heavily utilize Internet-based strategies including ReseachMatch.com, social media (i.e., Facebook, Twitter) and other social networking sites. We may recruit via flyer at primary care clinics. See Appendix 5 StandUPTV Flyers.

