2	30	YES	NO	YES
3	30	YES	YES	NO
4	30	YES	NO	NO
5	30	NO	YES	YES
6	30	NO	NO	YES
7	30	NO	YES	NO
8	30	NO	NO	NO

Table C3-1. Experimental conditions for optimization trial.

Intervention: The StandUPTV app is a basic self-monitoring application where participants can view their daily sedentary screen time habits (minutes of streaming video services such as Netflix, YouTubeTV, and SlingTV; minutes of physical activity and sedentary time). The app also includes three additional components: (a) a sedentary screen time limiting feature (LOCKOUT) which will disable tablet and Wemo plugs once they reach a target of 50% of their baseline sedentary screen time for the week of observation has been reached; (b) app-based prompts (TEXT i.e., prompts generated through StandUPTV) that provide personalized content based upon length of most recent sedentary screen bout and time of day (see Table below for examples); (c) feedback related to physical activity and the ability to earn additional sedentary screen time through physical activity above their 50% limit (EARN), defined as 10 minutes of moderate physical activity earns 20 additional minutes of sedentary screen time, depending on baseline levels of activity. Physical activity will be monitored continuously via Fitbit.

Table C7.2.3-1. Example prompts.				
SST bout	Time of			
length	day	Prompt examples		
>60 min	PM	Break up the binge! Try taking a break from the show. You will feel more alert when you return.		
15-60 min	PM	Let's multi-task! Stay productive with simple chores while you watch your favorite show.		
<15 min	AM	<no prompt="" sent=""></no>		

Participants will be then be instructed to use the StandUPTV application at their discretion over the next 16 consecutive weeks. They will be provided a telephone/email hotline supported by our study staff to address any technical questions they may encounter during study participation and will have check in calls periodically.

Interim & Final Assessment: Assessments will take place at week 8 (interim) and week 16 (final) to once again record 7 days of accelerometry data with the ActivPAL and GENEactiv devices and to assess via behavioral questionnaires the response to intervention components (see Data Collection/Outcomes table below). Exit interviews & User burden scale will be conducted interview style when possible and will be audio and video recorded via Zoom video conferencing platform (see Appendix 7 Exit Interview & User Burden Scale).

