C9-1. Data Collection/outcomes.

			Baseline	Interim	Post
Outcome	Measure	Week	0	8	16
Primary	Sedentary screen time, min/wk (app+activPAL)		•	•	•
outcome					
Proximal	Barriers, outcome expectations, and self-efficacy for SST		0	0	0
mediators					
	MVPA, min/wk (activPAL)		•	•	•
	24h behavioral composition (activPAL, ACT24)		•	٠	٠

Displacement effects/causal factors	Sleep (GENEActiv) Dietary intake (24-hr recall)	• 0	•	•
Health risk	Weight, body fat percentage, and waist circumference	•	•	•
User- experience	Application usage User burden	•••	•••	•••
•	Exit interviews			0

○Survey- or interviewer-administered; ●Device-based measure; SST = Sedentary screen time

Screen Time Surveys: Participants will be sent a sleep log each day via REDCap and asked to record information about their sleep habits and quality for the 7-day assessment periods (Appendix 8 Sleep log). They will also complete two ACT24 surveys, a mobile previous day recall (Appendix 10 ACT24 Instrument). Participants will be asked to record a screen shot of their screen time use from their phones and upload this at each time point. The purpose of this is to inform the data of any additional screen time that was consumed on their personal phones inadvertently. Each survey is expected to take between 15-30 minutes.

Compensation

Participants who complete the entire study protocol will receive up to \$100.00 over the course of the study to compensate for their time and effort completing the assessments. They will get to keep the Fitbit issued to them for use in the study (~\$130 value). Gift cards will be issued via the Tango website, this website will allow participants to pick from a number of different retailers. Any payments made to a single individual totaling \$600 or more will be reported to the tax unit of Financial Services.

Complete baseline assessment: \$40

\$10 for setup of devices completed with study staff. \$30 for wearing activity monitors and, completing questionnaires, the ACT24 diaries, the diet diaries, and responding to >75% of the text messages.

Complete 8-week assessment: \$30

\$30 for wearing activity monitors and completing questionnaires, the ACT24 diaries, and responding to >75% of the text messages.

```
Complete 16-week assessment: $30 + Fitbit (~$130 value)
```

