\$30 for wearing activity monitors and completing questionnaires, the ACT24 diaries, the diet diaries, and responding to >75% of the text messages. Participants who complete the study will also be allowed to keep the Fitbit utilized for this study (~\$130 value).

Risk to participants

In-person visits were initially proposed for this study but, due to the COVID-19 pandemic, in-person visits have been eliminated. Investigators will conduct non-contact participant visits to reduce the risk of transmitting COVID-19 between study staff and participants. Devices will be cleaned and disinfected between participants.

There is a very minimal risk that a device or devices the participant is wearing may cause them discomfort such as skin irritation. They are free to remove any device if they feel that it causes them a problem. There is a small risk of psychological discomfort when answering questions of a somewhat personal nature. These risks are minimized by informing subjects that responses are voluntary and that there will be no negative consequences in withholding responses. Participants in the EARN group will be asked to increase their time in

10-minute bouts of exercise. There is some risk of muscle soreness and injury when starting to exercise. The educational materials in this group will include information on starting slowly and building up activity.

Potential direct benefits to participants

There are no direct benefits of this study. Participants may become more aware of their screen viewing habits and their activity levels by participating.

Privacy and confidentiality

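### The protocol names soreness, injury and skin irritation as risks, but the outcomes table and SAP plan no harm measure or summary by component, so EARN could be selected on screen time alone.

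*Protocol*

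**What the plan says.** The protocol's section on risk to participants names two physical harms.

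- **Exercise, tied to EARN:** "There is some risk of muscle soreness and injury when starting to exercise". The stated response is educational: "The educational materials in this group will include information on starting slowly and building up activity".
- **Worn devices, all conditions:** "There is a very minimal risk that a device or devices the participant is wearing may cause them discomfort such as skin irritation". The stated response is freedom to stop wearing the device: "They are free to remove any device if they feel that it causes them a problem".

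Neither response records anything. In Table C9-1 the only row labelled as health risk is "Weight, body fat percentage, and waist circumference". The other rows cover screen time, mediators, activity, the 24-hour composition, sleep, diet and user experience.

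During the 16 weeks participants have a "telephone/email hotline supported by our study staff to address any technical questions they may encounter during study participation", and the same sentence adds periodic check-in calls whose content is not described. The Zoom visits under Body Composition Measurements are there to support those measurements.

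The SAP contains no safety analysis. Its Power Analysis section gives one optimization criterion, a 60 min/day reduction in sedentary screen time.

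**The concern.** The trial exists to decide which components belong in an optimized package. EARN is the component for which the protocol itself anticipates injury, in adults enrolled because they are insufficiently active. If no listed measure asks about injury and no analysis summarises it, EARN will be judged on benefit alone.

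This cannot be repaired at the analysis stage. Reports that participants happen to volunteer have no defined denominator, recall period or wording, and they depend on who was prompted to think about the problem. EARN participants receive material about starting exercise; the others are not described as receiving it. It is plausible, though not documented, that they would mention soreness more readily, in which case an EARN versus no-EARN contrast in volunteered reports would partly reflect prompting. Only a question put identically in all eight conditions gives rates that can be compared.

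**Working it through.** **1. The plan's own figure.** The documents give no harm rate and no precision target for harms. The only power figure is .80 for a main effect on screen time (N = 200, d = 0.4, α = .05). Unadjusted, with 100 per side and a two-sided test: Φ(0.4/√(2/100) − 1.96) = Φ(0.868) = 0.807, which reproduces it. With the stated r = .3 used in ANCOVA, the SD factor is √(1 − 0.09) and power is 0.843. Nothing in the present point depends on this.

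**2. Where a harm could be captured.**

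| Place | Stated content | Harm item? |
|---|---|---|
| Table C9-1, health-risk row | Weight, body fat, waist | No |
| Table C9-1, other rows | Behaviour, mediators, sleep, diet, usage | None listed |
| User burden scale; exit interview | Appendix 7, not supplied | Cannot be checked |
| Baseline survey battery | Appendix 15, not supplied | Cannot be checked |
| Hotline | Technical questions | No |
| Check-in calls | Not stated | Not stated |
| Zoom measurement visits | Help with body measurements | Not stated |
| Investigator contact given at consent | General contact | Volunteered only |
| Tracking system | Can hold medical information and notes | No form or schedule |
| SAP | Screen-time effects and power | No |

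**3. Numbers exposed.** EARN is given in conditions 1, 2, 5 and 6: 4 × 30 = 120 enrolled, against 120 without it. The SAP's final sample of 200 (25 per condition) gives 100 against 100. Each LOCKOUT × EARN cell has 2 × 30 = 60 enrolled, or 2 × 25 = 50 completers.

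**4. What systematic questions could show.** All event rates below are assumptions.

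*Zero events, one-sided 95% upper limit,* 1 − 0.05^(1/n):
- n = 120: 2.47%
- n = 100: 2.95%
- n = 60: 4.87%

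*Chance of seeing at least one event among 120,* 1 − (1 − p)^120:
- p = 0.5%: 45%
- p = 1%: 70%
- p = 2%: 91%
- p = 5%: 99.8%

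*95% half-width for the difference, 10% in both groups,* 1.96 × √(2 × 0.1 × 0.9/n):
- n = 120: 1.96 × 0.0387 = 7.6 points
- n = 100: 1.96 × 0.0424 = 8.3 points

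*Power, two-sided α = .05,* normal approximation with pooled variance under the null:

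| Assumed rates | 120 per side | 100 per side |
|---|---|---|
| 5% vs 10% | 0.31 | 0.27 |
| 5% vs 15% | 0.74 | 0.66 |
| 10% vs 20% | 0.58 | 0.51 |
| 10% vs 25% | 0.87 | 0.80 |

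The data would describe rates and reveal large differences. They would not support a formal safety test.

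**The case against.** The strongest reply is that absence is not proven. The user burden scale (weeks 0, 8 and 16), the exit interview and the survey batteries sit in appendices that were not supplied, and any of them might contain a harm item. Contact is also wider than the hotline: there are check-in calls, Zoom visits, investigator contact details given at consent, and a tracking system that can store medical information. The named risks are mild. All of this stands, and it limits the point to planned, systematic data. It does not remove the point, because no source in the supplied text is assigned to harms and the SAP has no summary to receive them.

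Four stronger readings are tempting and are not supported.

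- *The credit rule contradicts the advice to start slowly.* The rule is an exchange rate, "defined as 10 minutes of moderate physical activity earns 20 additional minutes of sedentary screen time", qualified by baseline activity, with the app used at the participant's discretion. A rate does not require any volume of exercise, so the two passages can both hold.
- *Earning back all the lost screen time measures exposure.* No passage asks for that, and the enforced cut applies only where LOCKOUT is assigned.
- *Unrecorded injuries bias the efficacy results.* An injury caused by EARN is part of EARN's effect as randomized; unrelated events are balanced in expectation and mainly add noise.
- *The exclusions should be re-checked during the study.* The criteria "major illness or pregnant, (3) physical activity contraindicated" are entry criteria. The protocol does not tie pregnancy to EARN, and re-screening would be a separate proposal.

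**Conclusion.** The point holds in a limited form. The protocol identifies soreness and injury from EARN and skin irritation from devices, while the outcomes table and SAP contain no measure of either and no summary by component. Subject to the appendices not supplied, EARN could be selected on screen time without planned harm data. It would be too strong to infer that no harm information could reach the team at all: incidental reports could, but not as comparable rates.

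The gain from correcting it is modest and descriptive: an upper limit of about 2.5% to 3.0% if no EARN participant reports an event, and a difference known to within about ±7.6 to ±8.3 points at an assumed 10% rate. These figures assume that everyone enrolled (120 per side) or every planned completer (100 per side) answers. This is a cheap improvement, not an error that threatens the primary analysis.

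**What to change.** First check whether the unsupplied appendices already hold suitable items. If not:

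1. Add to the week-8 and week-16 REDCap surveys, worded identically in all eight conditions: (a) injury or soreness that limited activity since the last assessment; (b) skin reaction to a worn device, and whether the device was removed.
2. Ask the same items at last contact with anyone who withdraws. Injury may itself lead to withdrawal, and items asked only of completers would miss those cases.
3. Send any positive answer to the site investigator.
4. Add to the SAP one descriptive table by EARN yes versus no, and by LOCKOUT × EARN, shown beside the efficacy results, with denominators and confidence intervals and no formal test.

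The cost is about a minute of participant time per assessment, some investigator follow-up, one survey alert and one table. No extra visit and no change in sample size is needed.

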Statistical Analysis Plan

Study Title: StandUPTV: Reducing Sedentary Screen Time in Adults NCT: 04464993

Document Date: April 11, 2022

Statistical Design and Power

Study Design. Table C4.1-1 outlines each experimental condition in this factorial experiment. All participants will be provided with the "core" intervention (i.e. education and basic STANDUPTV app) and randomized to none (i.e., app-based self-monitoring only), one, two, or all three of the intervention components. For example, a participant randomized to experimental condition 1 would get all intervention components, whereas a participant randomized to experimental condition 5 would receive only the TEXT and EARN components. This design should not be viewed as an 8-arm RCT where adequate power is required to detect all between-arm differences. Instead, in a factorial experiment, conditions are combined in highly efficient ways to produce estimates of main effects and interactions (i.e., synergistic/antagonistic responses to different combinations of components). Our design will test three main effects (LOCKOUT, TEXT, EARN), three 2-way interactions (LOCKOUT x TEXT, LOCKOUT x EARN, TEXT x EARN), and one 3-way interaction (LOCKOUT x TEXT x EARN).

opumization that.				
Exp				
Condition	n LOCKOUT		TEXT	EARN
1	25	YES	YES	YES
2	25	YES	NO	YES
3	25	YES	YES	NO
4	25	YES	NO	NO
5	25	NO	YES	YES
6	25	NO	NO	YES
7	25	NO	YES	NO
8	25	NO	NO	NO

Table C4.1-1. Experimental conditions for optimization trial.

Power Analysis. We aim to enroll 240 participants to achieve a final sample of 200 (20% dropout; n=25 per condition) for the 16-week intervention period. For ANCOVA models under the **Primary Aim**, N=200 will afford power of .80 to detect moderate main effects (d = 0.4) for each of the intervention components (LOCKOUT, TEXT, and EARN) and resultant two- and three-way interactions, assuming a modest baseline to post-intervention correlation (r=.3) and α =.05. We have chosen to power this study on a Cohen's d effect size = 0.4 as this represents a 60 min/day reduction in sedentary behavior observed in a previous using the activPAL (**C2.2**). This effect size estimate is conservative compared to much large effects (d > 1.0) from previous SST trials; however, our power is representative of achieving our statistical power to detect our optimization criteria of reducing SST by 60 min/day.

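### The 20% dropout in the SAP does not fit its own counts: 240 to 200 is 16.7%, and 20% dropout from 240 leaves 192, with little effect on main-effect power

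*SAP*

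**What the plan says.** The Power Analysis paragraph of the SAP gives the recruitment target, the final sample, the dropout rate and the cell size together: "enroll 240 participants to achieve a final sample of 200 (20% dropout; n=25 per condition". It then bases the power claim on the final sample: "N=200 will afford power of .80 to detect moderate main effects (d = 0.4". That claim assumes a baseline to post-intervention correlation of .3 and an alpha of .05. Whether the test is one- or two-sided is not stated, nor is the SD to which d is scaled.

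The protocol gives the same enrolment under Number of participants: "Approximately two hundred and forty (240) participants will be enrolled", split 120 and 120 between the two sites. Its allocation table ("Table C3-1. Experimental conditions for optimization trial") has 30 in each of eight conditions. The matching SAP table, C4.1-1, has 25 in each.

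**The concern.** Enrolment, final sample and dropout rate are tied by one equation, so any two fix the third. Here 240 and 200 imply a rate other than 20%, and 240 and 20% imply a final sample other than 200.

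The power claim rests on the final sample. A reader who monitors retention against this plan would take a 20% loss as within allowance, although at that loss the trial has already fallen short of 200 and, on average, of the 25 per condition in Table C4.1-1. What has to be settled is whether the shortfall costs enough power to matter.

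**Working it through.** **Inputs.** Enrolled 240, final 200, dropout 20%, 25 per condition, d = 0.4, power .80, r = .3, alpha .05 (SAP, Power Analysis); 240 enrolled and 30 per condition (protocol, Number of participants and Table C3-1). A two-sided test is assumed.

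**Counts**

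- Cells to totals: 8 × 30 = 240 and 8 × 25 = 200. The tables agree with the stated totals.
- Dropout implied by the counts: 1 − 200/240 = 16.7%. Per condition: 1 − 25/30 = 16.7%.
- Final sample implied by 20%: 240 × 0.80 = 192. Per condition: 192/8 = 24, the same as 30 × 0.80.
- Enrolment needed for 200 completers at 20%: 200/0.80 = 250, which is 31.25 per condition; equal whole cells need 8 × 32 = 256.
- 200 × 1.2 = 240. Inflating by 1.2 instead of dividing by 0.8 gives the SAP's number exactly. Rounding 16.7% up to 20% would leave the same text, so the cause is not proven.

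**Main-effect power.** Each main effect compares half the sample with the other half. With baseline as covariate:

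ncp = d × √N / 2 / √(1 − r²), df = N − 9 (eight condition means and one covariate), noncentral t, two-sided alpha .05.

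Setting r = 0 gives the power when d is already on the covariate-adjusted SD, or when the covariate brings no gain.

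| N | r | ncp | Power at d = 0.4 |
|---|---|---|---|
| 200 | 0 | 0.4 × 14.142 / 2 = 2.828 | .804 |
| 200 | .3 | 2.828 / 0.954 = 2.965 | .839 |
| 192 | 0 | 0.4 × 13.856 / 2 = 2.771 | .787 |
| 192 | .2 | 2.771 / 0.980 = 2.828 | .803 |
| 192 | .3 | 2.771 / 0.954 = 2.905 | .824 |

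The SAP's .80 at N = 200 is reproduced by the row without covariate gain (.804). With r = .3 on the raw SD the same sample gives .839.

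**Margins**

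- At N = 192 with d on the raw SD, power reaches .80 once r is about .18 (.178).
- Completers needed for .80: 181 with r = .3 on the raw SD, so 240 tolerates 1 − 181/240 = 24.6% dropout; 199 without the gain, so 240 tolerates 1 − 199/240 = 17.1%.
- Smallest d for .80 at N = 192: .388 with r = .3 on the raw SD; without the gain, .388/0.954 = about .407.
- In minutes: the SAP equates 60 min/day with d = 0.4, which implies an SD of 60/0.4 = 150 min/day, a figure it does not state. On that SD, .388 is 0.388 × 150 = about 58 min/day.

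**The case against.** The strongest reply is that nothing operational is wrong. Every head count agrees across the two documents and one percentage in brackets does not. On the SAP's stated r = .3 with d on the raw SD, a true 20% loss still leaves .824, and enrolment of 240 tolerates 24.6% dropout before power falls below .80. Power drops below .80 only if d is on the adjusted SD or r is under about .18, and at worst the gap is about 1.3 points (.787 against .80). All of this stands, and it limits the weight of the point. It does not reconcile the three numbers.

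Two readings might rescue the 20%. It could be meant relative to completers (40/200 = 20%), but neither document defines dropout that way. The protocol calls its enrolment figure approximate, but the SAP sentence states 240 without that qualifier.

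Two cautions also stand. The replacement figures of about .82 and 0.39 hold only for d on the raw SD. The 58 min/day conversion borrows an SD implied by a sedentary-behaviour effect in an earlier study, whereas the primary outcome here is sedentary screen time. It is illustrative only, and the conclusion does not depend on it.

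**Conclusion.** The inconsistency is real and follows from the plan's own figures. The stated counts mean 16.7% dropout; the stated dropout means 192 completers (24 per condition), 8 fewer, or 4% below the 200 on which power is quoted.

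The effect on main-effect power is small: about 1.5 points, from .839 to .824, if d is on the raw SD with r = .3; or from .804 to .787 if d is on the adjusted SD, which puts it just under the claimed .80. These figures assume a two-sided test and equal loss across conditions. They cover main effects only; interaction power was not needed for this point. The sentence should be corrected, but the error does not call the size of the trial into question.

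**What to change.** Keep 240 enrolled and change one figure in the Power Analysis paragraph:

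- **Either** give the tolerated dropout as about 16.7%. The final sample of 200, Table C4.1-1 and the power statement then stay as they are.
- **Or** keep 20%, restate the final sample as 192 (24 per condition), update the n column of Table C4.1-1, and restate main-effect power at d = 0.4: about .82 if d is on the raw SD with r = .3 (smallest d for .80 about 0.39), or about .79 if d is on the adjusted SD (smallest d about 0.41).

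In either case, say whether the test is two-sided and which SD d is scaled to, since that decides whether .80 has a margin or is only just met. The cost is about one sentence, plus one table column under the second option, and no added enrolment. Keeping both 20% and 200 completers would instead need 250 enrolled (256 for equal cells), which the small loss of power does not seem to justify.

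### The SAP names only a baseline-to-post ANCOVA sized on 200 of 240 participants, with no analysis set, missing-data method or role for week-8 screen time; dropout related to on-study viewing could bias a component's estimate

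*SAP*

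**What the plan says.** The SAP, under Power Analysis, enrols 240 "to achieve a final sample of 200 (20% dropout; n=25 per condition"). It refers to ANCOVA models for the Primary Aim and gives power of .80 for d = 0.4 at N = 200, "assuming a modest baseline to post-intervention correlation (r=.3") and alpha .05. The effect size was chosen "as this represents a 60 min/day reduction in sedentary behavior observed in a previous using the activPAL", and the same paragraph refers to "our optimization criteria of reducing SST by 60 min/day". No other primary model is named. Neither document defines an analysis set, a method for missing week-16 SST or a sensitivity analysis.

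The protocol collects more than the ANCOVA uses. Under Interim & Final Assessment: "Assessments will take place at week 8 (interim) and week 16 (final"). Table C9-1 marks the primary outcome, "Sedentary screen time, min/wk (app+activPAL"), at weeks 0, 8 and 16. Under Device Setup (SV2), the home kit records screen time throughout the study.

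Under Intervention, LOCKOUT is a feature "which will disable tablet and Wemo plugs once they reach a target of 50% of their baseline sedentary screen time", and EARN gives "the ability to earn additional sedentary screen time through physical activity above their 50% limit (EARN").

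**The concern.** An ANCOVA of week 16 on baseline, with nothing said about missing values, analyses only people who have a week-16 value. The plan itself expects to lose 40 of 240 (240 to 200) or 48 of 240 (20%). Such an analysis adjusts for dropout related to baseline SST. It does not adjust for dropout related to how much people were watching during the trial.

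The interventions make that second kind of dropout plausible. LOCKOUT switches devices off at half of a person's own baseline. EARN offers a way to regain time, so conditions 3 and 4 (60 of 240) have the limit without that relief. If the people who leave under LOCKOUT differ in viewing from those who stay, and the same does not happen to the same extent without LOCKOUT, the LOCKOUT main effect is shifted. Week-8 SST is the scheduled measurement best placed to reduce the shift, and the SAP gives it no role. With nothing specified, completer, imputation and repeated-measures analyses also all remain open after the data are seen.

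**Working it through.** **The plan's own figure.** A main effect compares 100 with 100. With d = 0.4 as 60 min/day, the implied SD is 60/0.4 = 150 min/day. Without the covariate, SE = 2 × 150/√200 = 21.2 and two-sided power is .807, which matches the stated .80. With r = .3, SE = 2 × 150 × √(1 − .09)/√200 = 20.2 and power is .843. Random loss of the planned size is therefore covered; the question is bias.

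**Inputs.** From the SAP: 240 randomised (30 per cell), r = .3, a 60 min/day effect and SD 150. That SD derives from activPAL sedentary behavior, not SST, and bias scales with it. Assumed, because the documents are silent: dropout 25% with LOCKOUT and 8.3% without (16.7% overall); log-odds of dropout of 0.3 to 0.5 per SD of week-8 SST, in LOCKOUT only; week 8 to week 16 correlation ρ of .5 to .7; r = .3 between baseline and each follow-up.

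**Size of the completer bias.** If dropout probability is p with log-odds slope g per SD of week-8 SST, the completers' mean week-8 SST shifts by about −g·p SDs. Carried to week 16 and adjusted for baseline, the bias is about −g·p·(ρ − r²)·SD:

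- g = 0.3: 0.3 × .25 × (.41, .51, .61) × 150 = 4.6, 5.7, 6.9 min/day.
- g = 0.5: 7.7, 9.6, 11.4 min/day.

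Simulation of the full 2×2×2 design (3,000 runs per row, all interactions fitted; negative means benefit overstated):

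| Log-odds per SD | Completer ANCOVA, ρ = .5/.6/.7 | Likelihood model with observed week 8 |
|---|---|---|
| 0.3 | −4.3/−5.4/−6.6 | 0.2/0.1/0.1 |
| 0.5 | −7.3/−9.2/−10.8 | 0.2/0.1/0.1 |
| 1 (extreme) | −13.3/−16.7/−19.9 | −0.1/−0.3/−0.2 |

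Reversing the slope, so that light viewers leave, gives 4.4 to 6.5 and 7.6 to 10.7 for log-odds −0.3 and −0.5. Against the SE: 4.3/20.2 = 0.21 and 10.8/20.2 = 0.53.

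**Same dependence at both levels, unequal rates.** The shift is then about g·(.25 − .083)·(ρ − r²)·SD. At ρ = .6 this is 3.8 (g = 0.3) and 6.4 (g = 0.5); simulation gave 3.8 and 6.0. With equal dependence and equal rates the bias is about zero.

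**Smaller variants.** Halving the SD in LOCKOUT gives 2 to 5 min/day at log-odds 0.3 to 0.5. Confining the dependence to conditions 3 and 4 (25% against 13.9%) also gives 2 to 5.

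**Where there is little bias.** Random dropout: under 0.5 min/day. Dropout on baseline SST only: under 0.5 when the LOCKOUT effect is constant. When LOCKOUT is modelled as a cap at half of each person's baseline, its effect varies with baseline, a common-slope ANCOVA is slightly misspecified, and the bias is about 0.4 to 3. Adding a baseline-by-LOCKOUT term to the ANCOVA brought this to about 0.5 or less.

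**Limits of week 8.** If half the dropouts have no week-8 value, 2.0 to 4.5 min/day remains (log-odds 0.3 to 0.5). If none has one, nothing is gained. If dropout depends on week-16 SST itself, the fraction remaining is 1 − [(ρ − r²)/(1 − r²)]², which is .80 at ρ = .5 and .55 at ρ = .7; simulation gave 56% to 80%.

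**Power.** Normal approximation: (60 − 10.8)/20.2 − 1.96 = 0.48, power .68; (60 + 10.8)/20.2 − 1.96 = 1.54, power .94. Simulated power was .66 to .77 if light LOCKOUT viewers leave and about .87 to .94 if heavy ones do, the latter inflated by bias.

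**The case against.** The strongest reply is that the SAP never says completers only. N = 200 appears in a power paragraph, and powering on the expected final sample is compatible with imputation or another analysis set. That stands: completer analysis is the natural reading, not an explicit statement. What is established is that the SAP leaves the matter open.

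Second, the size rests on invented inputs: the dropout split, the log-odds, the week-8 correlation, and an SD borrowed from a different behavior. That also stands. The non-extreme figures are half a standard error or less.

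Third, a reader might infer a power loss from the .66 to .77. The documents do not support that. A limit at half of baseline points, if anywhere, to heavy or most-restricted viewers leaving, which raises apparent power. In re-runs with LOCKOUT modelled as a cap, completer power stayed at .94 or above even when light viewers left. A reader might also infer that the wrong component would be retained, but the SAP gives no rule comparing an estimate with the 60 min/day criterion.

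Fourth, choosing a repeated-measures model over imputation from the continuous app record is partly preference. It is. The scheduled week-8 outcome is the simpler basis for the primary analysis; the app record matters most for people who leave before week 8 and belongs in a sensitivity analysis.

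**Conclusion.** The point holds as a cheap improvement. The omissions are plain in the text. Bias arises if dropout depends on on-study SST and either the dependence or the dropout rate differs by component level. Neither condition is documented; both are plausible for LOCKOUT. On the stated assumptions the shift is about 4 to 11 min/day in either direction. It is negligible under random dropout and small, though not always zero, if dropout depends only on baseline. Week 8 removes nearly all of it when observed and when data are missing at random, part of it if dropout depends on week-16 SST, and none of it for dropouts without a week-8 value. It would go too far to say that the trial's estimates will be biased, or that its power is inadequate.

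**What to change.** State in the SAP:

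1. All randomised participants are analysed as assigned.
2. The single primary analysis is a likelihood-based repeated-measures model of SST at weeks 8 and 16, with baseline SST by time, a centred baseline-by-LOCKOUT term by time, effect-coded factors and their interactions by time, and unstructured covariance. The week-16 contrasts are primary. Note that participants with neither follow-up add no outcome data.
3. Dropout is reported by component and by timing (before or after week 8), which shows how far week 8 can help.
4. Sensitivity analyses only: complete-case ANCOVA; multiple imputation using app-tracked SST; and a delta adjustment by component. Each 60 min/day of delta in LOCKOUT dropouts moves the LOCKOUT effect by 60 × .167 = 10 min/day at 16.7% dropout and 60 × .25 = 15 at 25%.

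The cost is SAP wording and minor programming, with no new data or visits. The downside is that the primary model relies on missing at random, and under equal random dropout it gains only 1 to 3 points of power.
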